#### 5.3. Data Analyses

Data for all patients who received at least 1 text message asking if they fasted the day prior, whether or not they completed all protocol requirements, will be included for analysis. Patient demographics, risk profiles, clinical characteristics, and baseline questionnaire results will be reported. All analyses will be performed using a modified intention-to-treat, excluding only patients who did not receive at least 1 text message asking if they fasted the day prior. Data can be missing for any day if the participant did not report adherence with daily fasting. For the main analysis, we will assume that days for which patients did not report adherence with daily fasting were non-adherent days. The primary analysis will compare days fasted per week between attention control and commitment device arms using a t test. Secondary analyses compare change from baseline in blood pressure and weight between arms using mixed effects regression models. Exploratory analyses will compare change from baseline in blood pressure and weight in patients who reported fasting  $\geq 4$  days/week versus those who reported fasting  $\leq 4$  days/week using mixed effects regression models.

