#### 4.4.1. Soft commitment device

Patients randomized to the commitment device arm will be asked to visit the Way to Health platform. There, they will identify a support person, a family or friend who they speak to frequently and who is invested in their health. They will then complete a series of questions intended to create implementation intentions. Specifically, they will pick a time for their fast to begin each 24-hour period and a time for their fast to end. They will also develop strategies to deal with hunger arising during a fast period. After this process, they will sign a contract pledging to adhere to the 16:8 time-restricted feeding dietary pattern, and acknowledging that their support person will receive a copy of the contract and weekly updates about their adherence to the regimen.

For the next 12 weeks, participants in this arm will receive reminder text messages two times daily via Way to Health: Once at the start of their fast period and once during the meal that they skip during the fast period. Each week, participants and their support partner will also receive a text message noting how many days in the previous week they successfully fasted for at least 16 hours. After the 12 week intervention, these text messages will stop, but for the entire 18-week period, participants in this arm will receive the same text messages as the attention control arm: A daily text message asking if they fasted for at least 16 hours over the previous 24 hours, and a weekly text message asking for weight and blood pressure results.

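### Every analysis is limited to randomised patients who were sent a daily adherence text, with no all-randomised analysis; the plan does not say whether the intervention arm's text waits for set-up that only that arm has

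*Combined protocol and SAP*

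**What the plan says.** Section 5.3 (Data Analyses) defines a single analysis population for all analyses, "excluding only patients who did not receive at least 1 text message asking if they fasted the day prior". Patients who did get a text are kept "whether or not they completed all protocol requirements, will be included for analysis". For unreported days the main analysis uses this rule: "we will assume that days for which patients did not report adherence with daily fasting were non-adherent days". The primary comparison of days fasted per week is a t test. For the secondary outcomes, "Secondary analyses compare change from baseline in blood pressure and weight between arms using mixed effects regression models". No second population and no sensitivity analysis is named.

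Under section 4.3, patients are randomised after giving baseline weight, blood pressure and questionnaires. What follows differs by arm:

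- **Control** (4.4.1 Attention control): patients are told to fast and then receive the daily question. No step for the patient to complete is described.
- **Intervention** (4.4.1 Soft commitment device): "Patients randomized to the commitment device arm will be asked to visit the Way to Health platform". There they name a support person and set fasting times and strategies. "After this process, they will sign a contract pledging to adhere to the 16:8 time-restricted feeding dietary pattern". The section continues "For the next 12 weeks, participants in this arm will receive reminder text messages two times daily via Way to Health", and later "for the entire 18-week period, participants in this arm will receive the same text messages as the attention control arm".

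The section does not say what starts the 18-week period, or what happens if set-up is never finished. Objective 1 (section 2) covers uptake as well as adherence.

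**The concern.** Entry to every analysis depends on something that happens after randomisation, and only one arm has patient-driven steps that might stand in its way. If the daily question is triggered by finishing set-up, an intervention patient who never finishes is never asked and leaves the analysis. A comparable control patient is texted regardless, stays in, and scores near zero under the missing-day rule. The arms are then no longer comparable, and the difference tilts towards the intervention. Failure to take up the device, which belongs to objective 1, would also go uncounted. With 17 patients per arm, two are 12% of an arm, and no planned analysis would show the effect.

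**Working it through.** **The plan's own figure.** Section 5.2 gives 90% power for 1 day/week with 17 per arm and a printed SD below 1.24. The 24 may be a citation number run on to a 1, so I use both 1 and 1.24. Alpha and sidedness are not stated; I assume 0.05. By the noncentral t with 32 df and noncentrality 1/(SD × √(2/17)), which is 2.92 at SD 1 and 2.35 at SD 1.24, two-sided power is 80.7% and 62.6% (one-sided 88.7% and 74.4%). The 90% is nearly met only one-sided at SD 1. That is a separate matter, and this point does not rest on it.

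**Two readings of the start of the daily question.**

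1. *It waits for set-up.* The text runs from contract to the 12 weeks of reminders to the 18-week period, so the clock may start at the contract.
2. *It starts automatically.* The daily question is described apart from the reminders, as the same messages control receives, and section 5.3 keeps patients regardless of protocol completion.

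Under reading 2 the shift is 0. The rest concerns reading 1.

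**Assumed inputs.** The documents give neither the number of non-completers nor mean adherence. I assume no true effect; ordinary patients at μ = 4 or 5 days/week; low engagers at 0.5; an average of m = 1, 2 or 3 non-completer types per arm of 17, the actual count varying by chance; and a fraction h of them low engagers, the rest ordinary. They are dropped from the intervention arm only.

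**Bias of the current set:** (m/17) × h × (μ − 0.5).

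- h = 1, m = 1: 3.5/17 = 0.21 to 4.5/17 = 0.26. For m = 2: 0.41 to 0.53. For m = 3: 0.62 to 0.79.
- h = 0.5 gives half of these: 0.10 to 0.13, 0.21 to 0.26, 0.31 to 0.40.

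**Bias if never-texted patients are scored 0:** −(m/17) × [0.5h + (1 − h)μ].

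- h = 1: −0.5/17 = −0.03 per patient.
- h = 0.5, m = 1: −2.25/17 = −0.13 to −2.75/17 = −0.16. For m = 3: −0.40 to −0.49.

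**Two-sided type I error** (simulated pooled t test, 40,000 replicates per setting, ranges over μ and SD):

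| Average non-completers per arm | Current set, h = 1 | Current set, h = 0.5 | Zero-scored, h = 0.5 | Common start day |
|---|---|---|---|---|
| 1 | 6-7% | about 5% | 5-6% | about 5% |
| 2 | 10-13% | 6-7% | about 7% | about 5% |
| 3 | 17-21% | about 8% | 9-10% | about 5% |

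With a common start day and everyone analysed, the mean difference is about 0 in every setting. If exactly one low engager per arm is fixed rather than random, the estimate still shifts by 0.21 to 0.26, but the error stays at 4-5%.

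**The case against.** The strongest reply is that the harm is conditional and the wording leans against it. The criterion is being sent a text, not replying or signing anything. The 12-week sentence governs the reminders, which need a chosen fasting time; the daily question needs no set-up input. Section 5.3 keeps patients whatever requirements they left incomplete. All of this stands as a fair reading. It does not close the gap, because that clause in section 5.3 covers patients already texted and does not say who is texted.

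Second, few patients are likely to be excluded. Each has registered, consented, completed questionnaires and returned baseline readings before allocation. This stands, and the larger error rates need about three of 17, for which the documents give no support.

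Third, failing set-up need not mean low adherence. A patient might stall on naming a support person and still fast at an ordinary rate. This also stands. It halves the bias in the h = 0.5 case and makes zero-scoring a poor lead remedy.

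A reader might infer that the plan does discard intervention patients who fail to engage, so that the primary result will be biased. The documents do not support that: no sentence makes the question wait for the contract. Nor can it be said that exclusions would fall in one arm only for every cause; a control patient who withdraws before the first text is dropped too.

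**Conclusion.** The point holds in conditional form. It is certain that every analysis is restricted by a post-randomisation event, that no all-randomised analysis is planned, and that the start of the intervention arm's daily question is undefined. Whether bias follows depends on that start. It is nil if texts are automatic. If they wait for set-up, it is about 0.1 to 0.8 day/week across the cases shown, against a design difference of 1, with two-sided error between about 5% and 21%. All of these sizes rest on assumed numbers of non-completers, their adherence and the SD. The count is probably small, so the lower end is the more plausible.

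The plan also conflicts on duration: 16 weeks in 4.4.1 Attention control and 4.5, against 18 in 4.4.1 Soft commitment device and 5.1. A reader might take this as further evidence of differential exclusion. It is not; it is a separate contradiction that affects how the windows are counted.

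The change is worth making before analysis. Confidence is medium, because the trigger is unstated.

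**What to change.** 1. Start the daily adherence question on the same day after randomisation in both arms, whether or not set-up is complete, and count the 12- and 18-week windows from that day. Reconcile the 16- and 18-week periods first.
2. Make the primary analysis all randomised patients as randomised, applying the missing-day rule to days asked but not answered.
3. If a patient is still never texted, score that patient as non-adherent only as a fallback, and report the current modified intention-to-treat analysis beside it as a sensitivity analysis. The rule in 5.3 is written for unreported days; using it for someone never asked extends it, and can overcorrect as shown above.
4. Report exclusions by arm with reasons.
5. In the blood pressure and weight models, include all randomised patients with any measurement, without zero-scoring.

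**Cost.** A platform trigger and a few sentences in the plan. If texts were already automatic, the two analysis sets nearly coincide. If they would have waited, the observed effect is smaller and more variable, and some early intervention days precede completion of the device. With a 1-day effect in patients who are not low engagers, and on average one low engager per arm (h = 1), the current set estimates 1.20 to 1.27 days and rejects in 70-85% of simulated trials, partly through bias. A common start day gives 0.94 day and 38-52%.

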#### 4.4. Study Arms

#### 4.4.1 Attention control

These patients will be instructed via text message and email to fast at least 16 hours per day every day. For the next 16 weeks, they will receive a daily text message via the Way to Health

platform asking if they fasted for at least 16 hours over the past 24 hours. If they fail to respond, reminder text messages will be sent. Once per week, they will receive a text message asking them to weigh themselves and check their blood pressure, and reply with the results via text message

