#### 4.5. End-of-Study Questionnaire Completion

At the end of the 16-week study period, patients will be alerted by the Way to Health platform to return to the website to complete an end-of-study questionnaire regarding their experience with IF.

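### The query period conflicts with the 18-week primary outcome (16 v 18 weeks), and unreported days count as non-fasting with no reply-rate summary or sensitivity analysis

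*Combined protocol and SAP*

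**What the plan says.** **Period.** Section 5.1 sets the primary outcome over 18 weeks, and section 3.1 implies the same length (12 weeks of intervention plus 6 of follow-up). For control, section 4.4.1 (Attention control) says "For the next 16 weeks, they will receive a daily text message via the Way to Health". For the other arm, section 4.4.1 (Soft commitment device) says "for the entire 18-week period, participants in this arm will receive the same text messages as the attention control arm". Section 4.5 says "At the end of the 16-week study period, patients will be alerted by the Way to Health platform". The last exclusion criterion in section 3.3.2 describes a study of six months.

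**Missing days.** Section 5.3 states, for the main analysis, "we will assume that days for which patients did not report adherence with daily fasting were non-adherent days". The primary test is a t test on days fasted per week. Neither section 5.3 nor any other section gives a second way of handling unreported days or a summary of reply rates.

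**Contact by arm.** Non-reply is chased: "If they fail to respond, reminder text messages will be sent". This stands in the control section but apparently covers both arms. In the commitment arm alone, "participants in this arm will receive reminder text messages two times daily via Way to Health", and each week "participants and their support partner will also receive a text message noting how many days in the previous week they successfully fasted". Of these extra messages the plan says "After the 12 week intervention, these text messages will stop".

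**The concern.** The two issues meet in the primary score.

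First, a fixed 18-week outcome needs 18 weeks of queries in both arms, and the text does not settle whether that happens. A day with no query cannot be reported, and section 5.3 does not say whether such a day counts as missing and therefore as zero.

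Second, the rule is neutral between arms only if patients who fasted are equally likely to say so in both. Silence on a day that was not fasted is scored correctly. Silence on a fasted day is scored wrongly. The commitment arm's weekly count is visible to a partner, and daily texts are the only adherence source listed in section 3.1. An unreported fasted day may therefore look like a failure to the partner, which is a reason to reply as distinct from a reason to fast. A difference in texting could then be read as a difference in fasting, or could hide one, and the plan has no pre-specified way to tell them apart.

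**Working it through.** **Inputs from the documents:** 17 per arm, target difference 1 day/week, stated power 90%, SD printed as below 1.24 (section 5.2); 18-week outcome (5.1); 12 weeks of arm-specific contact (4.4.1). **Assumed:** fasting rates, reply rates, two-sided 5% test, and an SD of 1, 1.24 or 2. The printed 1.24 may be 1 followed by a citation number, so both are used.

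**The plan's own figure.** With a noncentral t, 17 per arm and a difference of 1, two-sided 5% power is 62.6% at SD 1.24 and 80.7% at SD 1. One-sided 5% at SD 1 gives 88.7% (89.8% by normal approximation). The stated 90% is thus approached only at SD 1, one-sided. Nothing below depends on it.

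**1. Period.** Let m be fasting days per week, equal in both arms, with full replies.
- Both arms 18 weeks: spurious difference 0.
- Both arms 16 weeks: spurious difference 0, but weeks 17 and 18 of the outcome do not exist.
- Control 16, commitment 18, unqueried days scored zero: m × 2/18. At m = 4 this is 0.44; at m = 5 it is 0.56.

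**2. Replying.** If replies are truthful, the expected score is m × s, where s = P(reply | fasted). With a gap in weeks 1 to 12 only, bias = m × (s1 − s0) × 12/18. The chance of a significant result favouring the commitment arm, with no true difference, is P(t > 2.037) on 32 df with noncentrality bias / (SD × √(2/17)). Nominal is 2.5%.

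| m | s1 v s0 | Bias, days/week | SD 1 | SD 1.24 | SD 2 |
|---|---|---|---|---|---|
| 5 | 90% v 85% | 5 × 0.05 × 12/18 = 0.17 | 6.8% | 5.7% | 4.2% |
| 5 | 90% v 80% | 5 × 0.10 × 12/18 = 0.33 | 15.5% | 11.5% | 6.8% |
| 4 | 90% v 85% | 4 × 0.05 × 12/18 = 0.13 | 5.7% | 4.9% | 3.8% |
| 4 | 90% v 80% | 4 × 0.10 × 12/18 = 0.27 | 11.4% | 8.8% | 5.7% |

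If a share f of silent days were fasted days in both arms, bias = 7 × (overall reply gap) × f × 12/18. At f = 0.5, gaps of 0.05 and 0.10 give 0.12 and 0.23; at f = 0, none.

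The 12-week secondary outcome, if scored by the same rule, is not diluted: 5 × 0.05 = 0.25 and 5 × 0.10 = 0.50.

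*Reversed gap.* True fasting 5 v 4 days, replies 85% (commitment) v 90% for 12 weeks, then 90% in both: (5 × 0.85 − 4 × 0.90) × 12/18 + 0.90 × 6/18 = 0.73. Equal 90% replies would show 0.90. Power at SD 1 falls from 72% to 55%.

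**3. What a tipping-point analysis would show.** Corrected difference = D + 7 × [(1 − r1) × q1 − (1 − r0) × q0], where r is the reply rate and q the fasting rate on silent days. Assume r0 = 0.80 and r1 = (12 × 0.90 + 6 × 0.80)/18 = 0.867. The hardest case for the commitment arm is q1 = 0.
- Estimate reaches zero: D = 0.5 at q0 = 0.5/(7 × 0.20) = 0.36; D = 1.0 at q0 = 1.0/1.4 = 5/7, which lies at the bound if control's replied-day rate is 5/7 and beyond it if that rate is 4/7.
- Significance lost: at SD 1 the critical difference is 2.037 × √(2/17) = 0.70, so D = 1.0 loses significance at q0 = (1.0 − 0.70)/1.4 = 0.21 (SD held fixed). D = 0.5 is not significant to begin with.

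The two thresholds differ widely, so both need reporting.

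**The case against.** On the period, the best reply is that this is drafting residue. The commitment section says that arm receives the same texts as control for 18 weeks, which most naturally puts control at 18 too. Section 4.5 speaks of patients without naming an arm, so if 16 weeks governs, it governs both. Either coherent schedule gives no spurious difference. Section 5.3 also describes missing data as a participant not reporting, which fits an unanswered query better than a day with no query. All of this stands. A reader might infer from the control section alone that control goes unqueried in weeks 17 and 18 and that the result is tilted towards the commitment arm. The documents do not support that as the intended design.

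On replying, the two daily texts are sent at the start of the fast and at the skipped meal. They prompt fasting, not answering. The prompt aimed at non-reply appears to apply to both arms and may narrow any gap. No reply rate is given, and the effect is modest at a 5-point gap or a larger SD. This also stands, and it leaves the partner-visible count as the main reason to expect unequal replying. A reader might infer that the rule inflates the commitment effect. The documents do not establish that: the direction is unknown, and scoring silence as non-adherent is a reasonable main analysis.

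The objection does not remove the need to settle the period or the absence of any check on the rule.

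**Conclusion.** The point holds in two limited parts.

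1. The stated durations contradict one another and must be reconciled. On a common 16-week schedule the primary outcome cannot be collected as defined. The 0.44 to 0.56 days/week artefact needs three things together: control alone stopping at 16 weeks, unqueried days scored as zero, and 4 to 5 fasting days. It is a conditional figure, not an expected bias.

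2. The missing-day rule has no accompanying check, although unequal replying is plausible. At 5 fasting days/week and a 5- to 10-point gap for 12 weeks, the shift is 0.17 to 0.33 days/week against a design difference of 1. If it favours the commitment arm, the false-positive chance in that direction is about 6% to 16% at SD 1 to 1.24 and 4% to 7% at SD 2, against 2.5%. The opposite gap hides part of a real effect. If silent days were truly not fasted, there is no bias.

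All reply and fasting rates are assumptions, as is the two-sided 5% level. The changes should be made, but nothing here shows that the planned comparison is in fact biased.

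**What to change.** 1. Reconcile sections 3.1, 3.3.2, both parts of 4.4.1, 4.5 and 5.1 so that both arms are queried and scored over the same period as the primary outcome. State in section 5.3 that silence after a scheduled query counts as non-adherent and that a day with no scheduled query is not scored.
2. Keep missing as non-adherent for the main analysis. Report reply rates by arm for weeks 1–12 and 13–18.
3. Pre-specify one tipping-point analysis that varies the fasting rate on silent days separately by arm, from 0 to that arm's own replied-day rate. Report where statistical significance is lost as well as where the estimate reaches zero.

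This addresses non-reply only; it cannot detect or bound untruthful self-report. The cost is wording, one table and one extra analysis of data already collected, and possibly a small change to the message schedule. The downside is slightly more analysis work and possibly a smaller or less certain estimate.

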# 3. Study Design

#### 3.1. General Overview

The IFAST study is a two-arm randomized controlled trial aimed at evaluating whether a soft commitment device increases uptake and adherence to an intermittent fasting dietary pattern compared with control in patients with hypertension and obesity. The study will randomize 34 patients with hypertension and obesity to a 12-week intervention employing a commitment pledge, involvement of a supportive partner, setting of implementation intentions, and multiple daily reminder text messages or to an attention control involving daily text messages alone.

Following the intervention, there will be a 6-week follow-up period (see study protocol figure below).

The study will be conducted using Way to Health, a research information technology platform at the University of Pennsylvania used previously for behavioral interventions.

After institutional review board (IRB) approval of the study, patients who meet the eligibility criteria will be approached in select cardiology clinics and invited to participate. Those who qualify and express interest will provide informed consent to the study procedures via the Way to Health platform. All patients will receive a blood pressure cuff and scale, which will be used to measure blood pressure and weight weekly. Within the Way to Health platform, patients will be randomized to the intervention or control arms. All other management decisions are completely at the discretion of the care providers. Data capture will include:

- **Baseline case report form** (for each patient) collecting clinical information abstracted from the medical record
- **Baseline survey** collected via the Way to Health platform including psychometric questions, dietary patterns, and experiences with weight loss and dieting
- Daily adherence to an intermittent fasting dietary pattern collected via self-report from text messages
- Weekly weight and blood pressure measurement collected via self-report from text messages

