#### 5. Statistical Methods

# 5.1 Primary and secondary outcome measures

The study's primary outcome measure is adherence to the IF regimen, captured via daily text message, over 18 weeks, expressed in days per week.

Secondary outcome measures will include:

- 1) Adherence to the IF regimen over 12 weeks
- 2) Change in systolic blood pressure from baseline to 12 weeks and 18 weeks
- 3) Change in weight from baseline to 12 weeks and 18 weeks

Exploratory analyses will compare change in blood pressure and weight in patients that were adherent to IF  $\geq$  4 days per week vs.  $\leq$  4 days per week

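### BP and weight are analysed by mixed models with no stated missing-data assumption and no sensitivity analysis for patients who stop texting, although the primary rule scores silence as not fasting

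*Combined protocol and SAP*

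**What the plan says.** All post-baseline outcome data come from the patient by text. Section 3.1 lists "Daily adherence to an intermittent fasting dietary pattern collected via self-report from text messages" and "Weekly weight and blood pressure measurement collected via self-report from text messages". The requests are separate: a daily question about fasting and a weekly one for the readings. Section 4.4.1 (Attention control) describes the latter: "Once per week, they will receive a text message asking them to weigh themselves and check their blood pressure". The device arm gets the same requests. Sections 3 and 4 describe no clinic measurement after baseline that would recover a missing reading.

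Section 5.1 makes the BP and weight endpoints secondary: "Change in systolic blood pressure from baseline to 12 weeks and 18 weeks" and "Change in weight from baseline to 12 weeks and 18 weeks". Objective 2 in section 2 rests on them.

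Section 5.3 deals with missing data for fasting only. It accepts that "Data can be missing for any day if the participant did not report adherence with daily fasting" and then sets the rule for the main analysis: "we will assume that days for which patients did not report adherence with daily fasting were non-adherent days". For BP and weight it gives one sentence: "Secondary analyses compare change from baseline in blood pressure and weight between arms using mixed effects regression models". Model terms, covariance structure, coding of time, missing-data assumption and sensitivity analysis are not stated. No expected rate of silence is given anywhere.

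**The concern.** A mixed model fitted by likelihood to the available readings is valid under missing at random: given arm and a patient's own earlier readings, the unseen readings behave like those of comparable patients who are still observed. The primary rule takes a different view of silence, namely that the patient is not fasting. If that view is right for a patient who falls silent for good, the readings before silence come from the fasting period and the unseen ones do not. Earlier readings then predict later ones too favourably, and conditioning on them does not repair this.

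The link matters only if fasting moves BP and weight. Section 1.2 reports reductions of 5-10 mmHg in SBP and about 3 kg in weight in small studies, and Objective 2 presupposes such an effect.

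Unequal silence between arms is plausible by design. Only the device arm gets two extra reminders a day for 12 weeks and a weekly report to a support partner, and either could change how long patients keep replying.

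**Working it through.** **Scale, and the plan's own figure.** Section 5.2 gives 17 per arm, SD 15 mmHg for BP and SD 5 kg for weight. The standard error of a difference in means is SD x sqrt(2/17): 15 x 0.343 = 5.14 mmHg and 5 x 0.343 = 1.71 kg. With 10 mmHg and two-sided 0.05 (assumed; the plan states no significance level), power is Phi(10/5.14 - 1.96) = 49.3%. This reproduces the plan's figure of about 50% for SBP. That figure is not in dispute; it sets the scale for what follows.

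**Formula.** Let m be the mean change while fasting and replying, and s the proportion silent by week 18 (subscripts D device, C control). Suppose silent patients are back at baseline by week 18 and the model in effect extrapolates the replying trajectory.
- Modelled change in an arm: m. True change: m(1 - s).
- Modelled difference: m_D - m_C. True difference: m_D(1 - s_D) - m_C(1 - s_C).
- Error (modelled minus true): s_D m_D - s_C m_C.

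**Weight.** Assume m = -3 kg in both arms. The size is taken from section 1.2, which gives no duration; the silence rates are assumptions.
- 30% silent in both arms: -3.0 modelled against -3 x 0.7 = -2.1 kg true in each arm. The difference is 0 either way.
- 20% device, 40% control: modelled difference 0.0; true (-3 x 0.8) - (-3 x 0.6) = -2.4 + 1.8 = -0.6 kg.
- 10% device, 30% control: modelled 0.0; true -2.7 + 2.1 = -0.6 kg.

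Simulation agrees with this arithmetic to within about 0.1 kg. It used random-slope models with piecewise week terms by arm, a last reply at weeks 4 to 15, return to baseline over 4 weeks, and assumed SDs.

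**SBP with a true device effect.** Assume m_C = -3 and m_D = -13 mmHg, so the modelled difference is -10.

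| Silent, control / device | True difference (mmHg) | Overstatement (mmHg) |
|---|---|---|
| 0% / 0% | -10.0 | 0 |
| 10% / 10% | -9.0 | 1.0 |
| 30% / 30% | -7.0 | 3.0 |
| 30% / 10% | -9.6 | 0.4 |
| 10% / 30% | -6.4 | 3.6 |
| 20% / 40% | -5.4 | 4.6 |

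With m = -8 mmHg in both arms, equal silence gives no error in the contrast. A 20-point imbalance gives 8 x 0.2 = 1.6 mmHg.

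**Does the model really behave this way?** A random intercept and slope model for SBP was fitted to simulated data, one run of 3,000 patients per scenario.
- Silence driven by the last observed reading (missing at random): -9.96 estimated against -9.72 true, and -9.26 against -9.11. These gaps are within simulation noise.
- Silent patients return to baseline at once: about 30% silent per arm, -10.69 against -7.04; about 42% control and 17% device, -9.50 against -8.94; about 17% control and 42% device, -10.12 against -4.94.

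**The case against.** A reader might infer that the two analyses contradict each other. The documents do not support that. The daily and weekly texts are separate requests, so a patient can ignore one and answer the other, and non-responders to the daily text get reminders. The scoring rule applies day by day to the main adherence analysis and fixes no BP or weight value. What remains is a tension between assumptions, confined to patients who stop texting altogether.

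A reader might also infer that the mixed model treats silent patients as doing as well as those still replying. It does not: it conditions on arm and on each patient's own readings, so a patient who was worsening before silence is not given the repliers' mean. That protection fails only where the readings before silence look good and the unseen ones do not.

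Nor can one say that the estimates are biased. The plan gives no silence rate, timing or rate of regain. The illustrative inputs are assumptions, not the plan's own, and under missing at random the bias is about nil.

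The size also counts against a strong claim. A 0.6 kg error is about 0.35 of the 1.71 kg standard error, and in that example it runs against the device. The outcomes are secondary, with stated power of only about 50%. This stands for weight with equal fasting effects. It is weaker for SBP with a real device effect, where equal 30% silence overstates the contrast by 3.0 mmHg (0.58 of the 5.14 mmHg standard error) and the worst row by 4.6 mmHg (0.89).

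**Conclusion.** The gap is real but moderate: a missing-data assumption left unstated for the only outcomes that serve Objective 2, with no check on it. If silence means that fasting has stopped, and fasting affects BP and weight, the mixed models may overstate within-arm change; in the weight example this is -3.0 against -2.1 kg. They may also misstate the between-arm contrast in either direction: a benefit of 0.6 kg missed when control patients fall silent more often, or an SBP effect overstated by 0.4 to 4.6 mmHg when the device works.

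These sizes rest on assumed silence of 10% to 40% per arm, assumed changes while fasting, and full return to baseline by week 18. If regain is gradual, week 12 would be less affected. The primary adherence analysis is untouched. This is a cheap improvement, not a flaw that invalidates the plan.

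**What to change.** In section 5.3:

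1. Keep the mixed model as the stated secondary analysis, and say that it assumes missing at random given arm and observed readings.
2. Pre-specify one sensitivity analysis of SBP and weight at weeks 12 and 18. Multiply impute readings after a patient's last reply, centred on that patient's own baseline (return to baseline), with variance taken from the observed data. Section 4.3 requires baseline measurements before randomisation, so every randomised patient should have the value needed.
3. Report weekly reply rates by arm, for the daily and weekly texts separately.
4. State the significance level, and describe a BP or weight effect as not robust if the sensitivity analysis changes its direction or its significance.

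One related point must be reconciled first, because it decides which week-18 readings exist. Section 4.4.1 gives the control arm texts for 16 weeks, while the device-arm text describes the same messages over 18 weeks and section 4.5 calls the study period 16 weeks. Read literally, controls would have no readings in weeks 17 and 18.

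The cost is a paragraph of SAP text and one extra analysis on data already collected. The return-to-baseline estimate is conservative if silent patients are still fasting, and more so at week 12 because it allows no gradual regain. It should be presented as a bound beside the main result, not as a replacement.
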